Study protocol

Title:	From short-term surgical missions towards sustainable partnerships A survey among members of foreign teams and local doctors involved in surgical missions.
Study Protocol number:	2019-05
Date of protocol approval:	May 15 th 2019, by the board of Global Surgery Amsterdam
Study type:	Survey The content of the survey is provided below in this study protocol
Initiating organization:	Global Surgery Amsterdam (GSA) www.globalsurgeryamsterdam.com
Collaborating organization:	ICOPLAST www.icoplast.org
General information:	Particularly in low- and middle-income countries (LMICs), surgical missions are conducted on a large scale to provide surgical care. Annually, an estimated 313 million US dollars is spent on surgical missions. Typical missions are short-term, lasting up to several weeks. However, currently we know very little about the actual impact of these missions, including patient outcomes and strategies to make missions more sustainable. Therefore we developed an online survey. It is a first step in identifying what is currently being done and what should be done according to the respondent's experiences. The answers are used to provide more clarity on today's practices of short-term missions and to provide recommendations for the future. The survey consists of 21 questions. Outcomes will be anonymized.
Participants:	Members of foreign teams and local doctors involved in surgical missions.
Start of distribution:	June 2019, by email within the network of GSA and ICOPLAST
End of enrollment:	October 2019
Ethical clearance:	Not required for this study type

A survey for international and local team members involved in surgical missions in LMICs.

Developed by ICOPLAST and Global Surgery Amsterdam

www.icoplast.org

www.globalsurgeryamsterdam.com

Background:

We all aim for improving outcomes of our patients all around the globe. Many of our patients suffer from conditions that can be treated with (reconstructive) surgery. Particularly in low- and middle-income countries, surgical missions are conducted on a large scale to provide this type of care. Annually, an estimated 313 million US dollars is spent on surgical missions. Typical missions are short-term, lasting up to several weeks.

However, currently we know very little about the actual impact of these missions, including patient outcomes and future strategies (Hendriks et al., 2019).

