Therefore we developed this questionnaire. It is a first step in identifying what is currently being done and what should be done, according to your valuable experiences in the field. Your data is used to provide more clarity on today's practices of short-term missions.

The questionnaire consists of 21 questions. Please select one answer, and further clarify in the comment box if applicable.

Note: we may ask additional questions in the future if you approve us to contact you.

Outcomes will be anonymized.

Your function *

- Nurse / physician assistant (Please specify below)
- Plastic surgeon
- Orthopedic surgeon
- General surgeon
- Other surgeon (Please specify below)
- Policy officer NGO (Please specify below)
- Board member NGO
- Other...

Q1. Name *

Short answer text

Q2. Age: *

Short answer text

Q3. Sex: *

Short answer text

Q4. Email address: *

Short answer text

Q5. Nationality: *

Short answer text

Q6. How many missions did you perform in your life? *

Short answer text

Q7. Country where you performed your last surgical mission: *

Short answer text

Q8. Name of the hospital and town: *

Short answer text

Q9. Name of the NGO that supported this mission: *

Short answer text

Q10. Country where this NGO is based: *

Short answer text

Q11. Please give points over the following potential activities of a visiting team
(more points means a more important activity) *

	1 point	2 points	3 points	4 points
Provide surgical equipment and consumables for the local team, also for use after the mission left				
Provide free treatments				
Treat patients yourself				
Facilitate teaching of local staff (doctors and/or nurses)				

Q12. Is there, in your opinion, an activity missing in question 11? (please explain what activity is important and why) *

Long answer text

Q13. Should medical registration in the host country be required for specialists performing short-term surgical missions? *

- Strongly agree
- Agree
- Neither agree or disagree
- Disagree
- Strongly disagree

Comments:

Long answer text

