Q14. When medical registration was required for your last mission, the process to obtain the documents was straightforward. *

- Strongly agree
- Agree
- Neither agree or disagree
- Disagree
- Strongly disagree

Comments:

Long answer text

Q15. What can you say about the collaboration between authorities in LMICs (like the Ministry of * Health, the district health management or the national surgical society) and visiting surgical teams?

- There is no collaboration and it should be developed as a priority
- Collaboration is present but improvement is needed
- Collaboration has no benefits nor disadvantages
- Collaboration will likely be more harmful than beneficial for the mission

Comments:

Long answer text

Q16. What should have a higher priority in the hospital of your last mission ? Teaching in anesthesia care or teaching in surgical care?

*

- Anesthesia care
- Reconstructive care
- General surgical care
- Other surgical care (please specify in comments)

Comments:

Long answer text

Q17. A structured follow-up strategy (>6 months) of patients is required for short-term surgical missions.

- Strongly agree
- Agree
- Neither agree nor disagree
- Disagree
- Strongly disagree

Comments:

Long answer text

Q18. One month after the mission, an official report on the outcome including all complications encountered is recommended for all surgical missions. *

- Strongly agree
- Agree
- Neither agree nor disagree
- Disagree
- Strongly disagree

Comments:

Long answer text

Q19. A written long-term strategy (>5 years) with clear goals, developed by the visiting team and the local actors together, is recommended at the start of a new project. *

- Strongly agree
- Agree
- Neither agree nor disagree
- Disagree
- Strongly disagree

Comments:

Long answer text

Q20. What would you suggest to improve the impact of short term surgical missions? *

Long answer text

Q21. Hereby I give consent to use this data for publication. The purpose of this publication is to provide more insight into short-term surgical missions

Yes

No

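### Q14 rates the registration process with no not-applicable option and no filter item, so genuine ratings are mixed with answers from people the question does not fit

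*Protocol*

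**What the plan says.** The Protocol sets out the questionnaire in full.

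- **Q14** asks for agreement with "When medical registration was required for your last mission, the process to obtain the documents was straightforward". The answers run over five levels from strong agreement to strong disagreement, with the midpoint "Neither agree or disagree", followed by a free-text comment box.
- **Q13**, the only other item on registration, asks "Should medical registration in the host country be required for specialists performing short-term surgical missions". That is an opinion, not a record of what happened.
- **Q6 to Q10** cover the number of missions, the country, hospital and town of the last one, and the supporting NGO and where it is based. None concerns registration.
- **The instructions** read "Please select one answer, and further clarify in the comment box if applicable". No skip rule is given. Q14 carries an asterisk that is never defined; its absence from Q17 and Q21 suggests that it marks required items.
- **The target group** is "members of foreign teams and local doctors involved in surgical missions", and the function list also admits policy officers and board members of NGOs.
- **The purpose** is stated as "It is a first step in identifying what is currently being done and what should be done".

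**The concern.** Q14 is conditional. Its opening word concedes that registration is not always required, yet the form does not record for whom it was. Some respondents will probably have had nothing to obtain: local doctors working in their own country, NGO officers, and visiting clinicians whose last mission needed no registration. If they answer, they have to choose a level of agreement. The midpoint, and possibly other levels, then holds both people with a view on the process and people with no experience of it.

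The wording also leaves open whether the respondent's own registration or the team's is meant. NGO staff or local hosts who handled the paperwork cannot tell whether they count.

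At stake is the survey's only evidence on how registration works in practice. Its percentages would rest on a denominator whose make-up is only partly known. The form also cannot show how often registration was required. That would be useful context for Q13, although Q13 can be reported as opinion without it.

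**Working it through.** The Protocol gives no figure on this point, so there is none to reproduce.

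**Step 1: can the status be found elsewhere?** Reading every item from the function question to Q21 finds no filter item, no skip instruction and no not-applicable option for Q14. The indirect routes are partial:

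| Respondent | What could identify them |
|---|---|
| NGO staff | Function question |
| Local doctors | Nationality (Q5) against country of last mission (Q7), approximately |
| Anyone who volunteers it | Optional comment box, or later contact if the respondent agrees |
| Visiting clinician, no registration needed | No coded field |

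**Step 2: bounds on agreement.** Let A be the share of all respondents seen to agree and p the share to whom Q14 does not apply. If all the non-applicable agreed, true agreement is (A − p)/(1 − p). If none did, it is A/(1 − p). The width is p/(1 − p). A and p are assumed values.

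- A = 0.60, p = 0.10: 0.50/0.90 = 55.6% to 0.60/0.90 = 66.7%; width 11.1 points.
- A = 0.60, p = 0.20: 0.40/0.80 = 50% to 0.60/0.80 = 75%; width 25 points.

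**Step 3: agreement against disagreement.** Assume a true split of 60% agree, 15% neutral and 25% disagree among those to whom Q14 applies. Agree/(agree + disagree) is then 0.60/0.85 = 70.6%.

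| Where the non-applicable answer | p = 0.10 | p = 0.20 |
|---|---|---|
| All at midpoint | 0.54/0.765 = 70.6% | 0.48/0.68 = 70.6% |
| All agree | 0.64/0.865 = 74.0% | 0.68/0.88 = 77.3% |
| All disagree | 0.54/0.865 = 62.4% | 0.48/0.88 = 54.5% |

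**Step 4: the midpoint.** With p = 0.20 and all of the non-applicable at the midpoint, it holds 0.15 × 0.80 + 0.20 = 0.32 of all answers. Of these, 0.20/0.32 = 62.5% are not ratings. The contrast in Step 3 is untouched in this case, but the plain agreement percentage falls from 60% to 0.60 × 0.80 = 48%.

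**The case against.** The strongest reply is that the form has an outlet and that the harm is small. Q14 has its own comment box, and respondents are told to clarify there. The country, hospital and NGO items could help sort answers by setting. The asterisk is undefined, so the item may be skippable. Every share used above is assumed, and the all-agree and all-disagree cases are mathematical limits. In particular, it is not obvious why someone who needed no documents would deny that the process was straightforward. This is a descriptive first-step survey in which no other item depends on Q14. Stating a denominator is also ordinary work for an analysis plan.

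Much of this stands. The size is unknown, the extreme cases are not forecasts, and the absence of a reporting rule from the Protocol is not itself a fault.

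The core point remains. Comments are optional, so silence does not distinguish a respondent who needed no registration from one who is truly neutral. If the item can be skipped, a blank cannot be told from ordinary non-response. Country and hospital do not show whether a given clinician had to register. An analysis plan can restrict the denominator only if the form collects the status, and it does not.

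**Conclusion.** The concern holds. Q14 as written cannot separate ratings of the registration process from answers by people who had none to rate, and later analysis can repair this only in part. The amount and direction of any distortion are not computable from the Protocol. The ranges shown depend on assumed non-applicable shares of 10% and 20%, an assumed 60% agreement and, for the contrast, an assumed 60/15/25 split. Reading the asterisk as a mandatory mark is also an assumption, but the defect remains on either reading. The consequence is limited to one descriptive item and does not invalidate Q13 or the survey. It should be fixed because the item is the only one on actual registration experience and the remedy is cheap.

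**What to change.** Either of two changes is enough:

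1. Add an answer to Q14 such as *Not applicable / no registration was needed*.
2. Put a filter item before it, for example *Did your last mission call for registration with the host country's medical authority? Yes / No / Don't know / Not applicable*, and show Q14 only to those who answer Yes. This also shows how often registration was required.

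In both cases, say whether the respondent's own registration or the team's is meant, and report Q14 among those to whom it applies, with that denominator stated.

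The cost is one answer option, or one tick-box item and a branch in the online form, and fewer respondents in the Q14 denominator. If answers have already been collected, the report should say that the Q14 denominator includes an unknown number of non-applicable respondents, and should not present the percentages as the experience of those who had to register.

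### Q15 offers no answer for collaboration that is present, beneficial and in no need of improvement, so its second option may be inflated by an unknown amount

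*Protocol*

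**What the plan says.** The Protocol contains the questionnaire itself, so the wording of Q15 is fixed there and is not left to an analysis plan. The stem begins "What can you say about the collaboration between authorities in LMICs" and goes on to visiting surgical teams. The four answers are:

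1. "There is no collaboration and it should be developed as a priority"
2. "Collaboration is present but improvement is needed"
3. "Collaboration has no benefits nor disadvantages"
4. "Collaboration will likely be more harmful than beneficial for the mission"

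A comment box follows. The introduction to the survey gives the response rule: "Please select one answer, and further clarify in the comment box if applicable". The General information section states the purpose: "The answers are used to provide more clarity on today's practices of short-term missions and to provide recommendations for the future".

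**The concern.** A closed single-choice item should hold a true answer for every view it is meant to count. In Q15 the state of collaboration (absent or present) and the judgement on it (to be developed, to be improved, neutral, harmful) are merged into single answers. One plausible combination, present and beneficial with nothing to improve, is left out.

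What is at stake is the reading of option 2. Q15 is the only closed item on collaboration with authorities, and a percentage saying that collaboration needs improvement is a natural output of it. That percentage could mix respondents who want improvement with respondents who only wanted to say that collaboration exists, and the closed counts cannot separate them. Elsewhere the form leaves more room: Q13, Q14 and Q17 to Q19 use five-point agreement scales with a neutral point, and the question on the respondent's function has an open choice.

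**Working it through.** The Protocol states no expected proportion or sample size for Q15, so there is no figure to reproduce. The check is a comparison of the answers with the missing view, followed by a bound in symbols.

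**Step 1. Answers set against the view *present, beneficial, no improvement needed*.**

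| Option | What it asserts | True for this respondent? |
|---|---|---|
| 1 | Collaboration absent | No, it denies presence |
| 2 | Present, needs improvement | No, on the need for improvement |
| 3 | Neutral | No, it denies benefit |
| 4 | Net harm | No, it denies net benefit |

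Fitting answers: 0 of 4. Answers stating presence: 1 of 4, and that one also states a need for improvement. Respondents who find collaboration adequate but still see room to improve are not affected, because option 2 is true for them.

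**Step 2. Effect of this group on option 2, with all other answers taken as correct.** Let p be the share of all respondents for whom option 2 is the right answer, s the share holding the missing view, f the fraction of s who tick option 2, and g the fraction of s who skip the item. The rest of s tick something else, such as option 3. Then

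recorded option 2 share among those answering = (p + f·s) / (1 − g·s).

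The excess over p is s·(f + p·g) / (1 − g·s). It is never negative. Since p ≤ 1 − s and f + g ≤ 1, we have f + p·g ≤ f + g − g·s ≤ 1 − g·s, so the excess is at most s.

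Illustration, with p = 50% and both values of s assumed:

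| Behaviour of the group | s = 10% | s = 20% |
|---|---|---|
| All tick option 3 | 50% | 50% |
| All skip the item | 0.50/0.90 = 55.6% | 0.50/0.80 = 62.5% |
| All tick option 2 | 50% + 10% = 60% | 50% + 20% = 70% |

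The second row shows that option 2 can be inflated even if nobody in the group ticks it.

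**Step 3. Why this gives no net range for the wish to improve.** Options 2 and 3 are not mutually exclusive. A respondent who thinks existing collaboration brings no benefit now, and should therefore be improved, can truthfully tick either. Let v be the share who hold that view and tick option 3. With no skipping, the recorded share is p + f·s, while the wish to improve existing collaboration is p + v. The difference, f·s − v, can have either sign. With assumed p = 50%, s = 10%, f = 1 and v = 20%, the recorded share is 60% and the wish is 70%. If the wish is meant to cover any call for better collaboration, option 1 belongs to it as well, and option 2 alone falls further short.

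**The case against.** The strongest reply has four parts.

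*The harm is conditional.* The Protocol names no option 2 proportion as an outcome and nowhere says that it will be read as demand. It describes the survey as a first step. This stands, and it limits the weight of the point. It does not remove the gap, since recommendations are to be drawn from the answers.

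*The comment box lets a satisfied respondent speak.* True, and Q20 invites open suggestions too. But comments are requested only where applicable, and they do not form a countable category.

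*The recorded share can be corrected.* A reader might infer that a recorded 60% with s = 10% means a true demand of 50% to 60%. The documents do not support this. The range needs every other error in the item to be zero, and the overlap of options 2 and 3 and the call for change in option 1 prevent that assumption.

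*Comments can supply the correction.* A reader might count option 2 respondents whose comment calls collaboration adequate without asking for improvement, and treat that count as a lower bound on misfits. It is not one. These respondents have already ticked that improvement is needed and have no reason to repeat it. Only an explicit statement that no improvement is needed identifies a misfit.

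It might also be inferred from the asterisk at Q15 that the item was mandatory and the group was forced into an answer. The document does not define the asterisk, and the point does not depend on it.

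**Conclusion.** The gap is certain from the text: Q15 has no true answer for a respondent who sees collaboration as present, beneficial and not in need of improvement, and no way to answer *other* or *don't know*. The option 2 share may therefore overstate the wish to improve existing collaboration. Taken alone, this group can leave option 2 unchanged or raise it, by at most s. The Protocol gives no value for s or for how the group would answer, so the size is unknown. The percentages shown above are illustrations on assumed inputs. The net error in option 2 as a measure of demand is not bounded, and its sign is not fixed. Severity is minor: one item of an exploratory survey, with a comment box as partial relief.

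**What to change.** **Before launch.** Add two answers to Q15: one for collaboration that is present with no improvement needed, and one *other / don't know*. Alternatively, split the item in two, one question on the current state (present and no improvement needed, present and improvement needed, absent, don't know) and one on the value of collaboration. The split also removes the overlap between options 2 and 3. The cost is a slightly longer item, or one extra closed question.

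**If answers are already collected** (distribution was planned from June 2019 and enrolment to October 2019). Report the counts for all four answers with their full wording. Do not present the option 2 share as measured demand for improvement. Report separately the number of option 2 respondents whose comment explicitly says that no improvement is needed, labelled as the identified misfits only. The cost is a reading of the Q15 comments and one caveat in the report, with no new data.

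### Q17 does not mark whether it asks about an existing rule or the respondent's opinion, so disagreement with it can mean two different things

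*Protocol*

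**What the plan says.** The protocol's General information entry gives the survey a double aim: "It is a first step in identifying what is currently being done and what should be done". It says that the answers will clarify today's practice and also serve "to provide recommendations for the future". The introduction shown to respondents repeats the double aim, "identifying what is currently being done and what should be done, according to your valuable experiences in the field", but on the use of the data it mentions only clarifying today's practice.

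Q17 reads "A structured follow-up strategy (>6 months) of patients is required for short-term surgical missions" and is answered from strongly agree to strongly disagree, with a comment box. Q18 (a report one month after the mission) ends "is recommended for all surgical missions". Q19 (a written joint strategy) ends "is recommended at the start of a new project". Both use the same type of scale and also have a comment box.

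Other items state plainly that an opinion is wanted. Q13 asks "Should medical registration in the host country be required for specialists performing short-term surgical missions". Q12 asks for the respondent's opinion in so many words, and Q16 asks what should take priority.

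**The concern.** Q17 is in the present indicative. It contains neither *should* nor a reference to opinion, and it does not say who does the requiring. A respondent may treat it as a claim about existing rules and disagree because neither the NGO nor the host country has such a rule. Another may treat it as a norm and agree because such follow-up ought to be required.

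Q17 is the only closed item on patient follow-up, and its answers are meant to feed recommendations. If a report that no rule exists is counted as opposition to having one, the recommendation rests on a misread answer. Later analysis cannot tell the two apart, because no other closed item asks whether follow-up was in place or required at the last mission.

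**Working it through.** The protocol states no expected proportion, sample size or power for Q17, so there is no figure to reproduce. The check compares wording.

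**1. How the form uses *required* and *recommended***

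| Item | Form of the statement | Tied to the last mission? | Sense |
|---|---|---|---|
| Q13 | *Should ... be required* | No | Norm, clearly marked |
| Q14 | *was required*, past tense | Yes | A rule that applied |
| Q17 | *is required*, present tense | No | Not marked |
| Q18 | *is recommended*, for all missions | No | Not marked, leans to norm |
| Q19 | *is recommended*, for a new project | No | Not marked, leans to norm |

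All five are answered on a five-step agree-disagree scale. Q14 uses it to collect an experience and Q13 to collect an opinion, so on this form the scale alone does not show which is wanted.

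**2. What each answer to Q17 would mean**

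- Read as a fact: agree means that such a rule exists, and disagree means that none does.
- Read as a norm: agree means that follow-up ought to be required, and disagree means that it ought not.

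A respondent who favours the rule but knows of none in force would disagree on the first reading and agree on the second. The same person with the same view can land on opposite sides of the scale.

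**3. Does the surrounding text settle it?** No. The introduction names both aims, and its sentence on the use of the data mentions only today's practice, which if anything leaves the factual reading open.

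**4. Size, as illustration only.** Let N be the percentage agreeing under the normative reading, F the percentage agreeing under the factual reading, and r the fraction who read the item as fact. Observed agreement is

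(1 - r) × N + r × F = N - r × (N - F).

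Assume N = 85 and F = 30, neither of which comes from the protocol. Observed agreement is then 85 - 55r:

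- r = 0: 85.0%, no shift
- r = 0.1: 79.5%, shift 5.5 points
- r = 0.2: 74.0%, shift 11 points
- r = 0.4: 63.0%, shift 22 points

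The shift is zero if r = 0 or if N = F, and it reverses if F exceeds N. The protocol gives none of the three quantities.

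**The case against.** The strongest reply is that an unanchored general statement with an agree-disagree scale is ordinary attitude-item wording, and most people will take it as a request for their view. When the form wants an experience, as in Q14, it uses the past tense and ties the item to the last mission. Q17 does neither. Each item also has a comment box, and Q20 invites free suggestions, so a respondent who disagrees because no rule exists can say so.

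Much of this stands. It makes the normative reading of Q17 the likelier one. For Q18 and Q19 it is stronger still: a recommendation for all missions, or at the start of any new project, has no natural factual referent. It does not clear Q17. The comment box is to be used only if applicable, and a respondent who sees one reading has no reason to explain it.

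Two stronger readings are tempting, and the protocol supports neither. A reader might infer that agreement on Q17 to Q19 *does* mix fact and opinion; the wording permits mixing but does not show that it occurs. A reader might also infer a spurious difference between foreign and local respondents. With the assumed figures above, r = 0.1 in one group and 0.4 in the other would give 79.5 - 63.0 = 16.5 points with no difference in opinion. That rests wholly on assumed values, disappears when r is equal in the two groups (including r = 0 in both), and concerns a comparison that the protocol does not state.

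**Conclusion.** The point holds for Q17 as an ambiguity of wording: a disagree answer can mean that no such rule exists or that the respondent opposes one, and the form gives no means of separating the two. For Q18 and Q19 it is a weaker matter of consistency. The size of any effect is unknown and may be nil. The conclusion rests only on the printed wording of Q13, Q14 and Q17 and on the stated double aim, not on the illustrative percentages. It is a cheap improvement to one item and does not undermine the survey as a whole.

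**What to change.** Before distribution, put Q17 in the style of Q13: open it with *In my opinion* and change *is required* to *should be required*. For consistency, use the same opening in Q18 and Q19 and change *is recommended* to *should be recommended*.

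If forms on the printed wording have already been returned, report them separately as agreement with the statement as printed. Do not present them as the share who want the rule or as the prevalence of current practice.

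The cost is three reworded stems on an online form and no added questions. If the change comes after distribution begins in June 2019, it splits the sample into two wordings that should not be pooled without comment, so it is best made beforehand.

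The rewording settles which question is asked but does not measure current practice on follow-up. If the sponsor wants that as well, it needs a separate factual item tied to the last mission.
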